**SIGNIFICANCE.** The current study proposes a scalable intervention designed to increase identification and linkage to CSC for adolescents involved in the JJS who present with psychosis spectrum symptomatology. Juvenile courts, and the JJS broadly, are increasing the proactive screening of youth for mental health symptoms. However, there is an inevitable lag between screening and an outpatient mental health appointment which, in turn, is followed by generally poor uptake of outpatient treatment. This application's approach is consistent with FOA language, specifically the NIMH interest in "better signal detection of psychosis onset, or symptoms suggesting high clinical risk of psychosis, within .... criminal justice agencies," as well as "methods to achieve expeditious referral of persons with first episode psychosis (FEP), or those at high clinical risk of psychosis, to an appropriate specialty care treatment program". As specified in the FOA, this planning grant application will also: "identify a baseline rate of DUP", as well as explore the occurrence of psychosis-spectrum symptoms among high risk JJ youth, "identify bottlenecks and gaps in the pathway to CSC care", and "develop and pilot test feasible strategies for substantially reducing DUP". The scientific premise of this research is supported by the need to develop more effective screening and linkage to service strategies during a youth's contact with the JJS, the virtual absence of such studies in the literature, and its enhancement by use of a conceptual model for implementation. Our study will provide data on screening delivered by JJS staff and improved linkage to follow-up mental health care as the clinical services mechanism hypothesized to reduce the DUI/DUP. As requested in the FOA, we will also "provide evidence of the association between those targets", i.e. latency to treatment linkage and engagement in treatment, and "the outcomes of interest (e.g., DIU/DUP, symptoms, and functioning)". In exploratory analyses, we will also assess potential moderators that may inform which youth most benefit from this screening/referral intervention, including adolescent sex, gender, race, ethnicity, and socioeconomic status, as well as service level factors, i.e., fidelity of JID and CSC staff to the referral process. This research also has the potential to directly inform clinical practices in JJS settings and has significant implications for scalability and dissemination. Scientific rigor is maintained by ensuring fidelity to the brief screening/referral protocol, study retention procedures, blinding of research assessors, data analytic strategies including missing data procedures, which are described in detail in the approach section below. Additionally, relevant biological variables, specifically sex, are considered in the

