Because there are several research projects being conducted in the RIFC JID, Co-I [name] has established a procedure whereby all families in the waiting room are approached by an RA and asked to sign a "consent to contact" form. If a parent signs this form, and the teen subsequently screens positive and qualifies for a study being conducted in RIFC after the JID intake worker administers the MAYSI-2/PQ-B, research staff will then meet separately with parent/caregiver and the juvenile to describe study procedures in detail and 1) obtain juvenile assent without parental presence (note: no juvenile will ever be sanctioned by the court for not agreeing or being unable to participate in the research study; see Human Subjects/RIFC Chief Judge Letter of Support), and 2) obtain written informed consent from the parent/caregiver. If the research team is unable to meet with the family while they are at their intake appointment, the family will be contacted by phone/text and an appointment, either at the RIFC or at the family home, to consent/assent the parent and teen, and conduct the baseline assessment. Consenting procedures will also include permission to access court records.

**Intervention condition overview.** The intervention will have two phases: 1) a Standard Care (baseline control) condition, followed by, 2) an Enhanced Referral/Linkage to Care condition. Because this is a roll-out trial, the two conditions will be compared using a non-randomized open trial design. **Design Consideration:** We decided against randomization due to the following reasons: a) use of front line workers, as opposed to research staff specifically employed for the purposes of the research study, could result in contamination across the two study conditions; b) randomization would create the potential for therapist characteristics having a primary effect on referral outcomes; and c) JJS administrators and staff, at this site have expressed concerns that randomization is an unacceptable practice in the JJS because it results in the denial of what is assumed to be a superior service, the Enhanced Referral condition, to 50% of the youth.

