**Fidelity to the Enhanced Referral/Linkage to Care condition.** We will have the CSC clinician, who will be employed by the research project but also work at the CSC, audiotape their conversation with the family in the enhanced referral phase of the study. The CSC clinician will use a hand-held audio recorder so that only the CSC clinician's portion of the conversation will be recorded. Fidelity will also be rated by interviewing the parent/caregiver at the baseline research assessment, which will typically occur within a week of the JID

appointment. Caregivers will be asked what the CSC intake worker said to them about scheduling a CSC appointment. The RA conducting the assessment will record verbatim the parent's responses. In both the clinician reported and parent reported data collection, fidelity will be rated by PI [name] and Co-Is [name] and [name] on a two-point scale (0= not satisfactory; 1= satisfactory). If there is disagreement, a consensus meeting will be held to resolve discrepancies in ratings.

**Baseline and follow-up assessment.** Families in both phases of the study will complete the same assessments at baseline and 3-month follow-up to gather data on treatment history, psychosis-spectrum symptoms, general psychiatric symptoms and functioning, as well as JJS contacts (see details below under Measures). In addition, at follow-up, we will interview families about barriers to treatment linkage and treatment satisfaction. The RA and Co-I [name] will be blind as to whether the families were seen for follow-up CSC or mental health care until after the interviews are completed.

We will also interview JID intake workers and CSC staff to assess both services and implementation factors related to referral process and completion. The baseline and follow-up assessment battery were designed to minimize participant burden and to thoroughly assess psychosis-spectrum symptoms. The follow-up assessment will be scheduled 3-months post-referral to the CSC. The 3-month follow-up period will allow us to assess whether high risk youth engage in treatment with the CSC or other mental

healthcare. Both baseline and follow up interviews will be conducted in-person and last approximately 1.5- 2 hours.

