Co-I [name] will administer the Structured Interview for Psychosis-risk Syndromes (SIPS), described below. She has received formal training and certification by SIPS developers to conduct the interviews, and she was trained to research quality reliability (ICC>.8) within her prior research team. She will administer all the SIPS interviews in order to maintain consistency across the two phases of the study as well as across participants. At baseline, when we will assess youth with both positive and negative screens, Co-I [name] will be "blind" to whether youth have screened positive or negative. At follow-up, she will know that all youth have screened positive on the MAYSI-2 and *PQ-B*, but the RA and Co-I [name] will instruct families not to disclose whether they followed through with the referral to the CSC or whether they have received any type of follow-up mental health care until after the assessment is completed.

**Training in assessment.** Training in the assessment protocol will occur during the first 2 months by Co-I [name], following procedures we used in other RCTs. Under Co-I [name]'s oversight, research staff conducting baseline assessments will also receive training on working in the JJS and on how to appropriately respond to logistical questions that participants' may have about the JJS. Co-I [name] will oversee the baseline assessment and Co-I [name] will oversee the follow-up assessment component of the protocol. If parents request it, the results of the evaluation will be shared with the CSC in both phases of the study.

**Procedures for mental health deterioration/safety concerns.** It is possible that some participants will report symptoms during their research assessment that may warrant additional mental health care. If any youth indicates serious psychotic symptoms or suicidal/homicidal thoughts, a safety plan will be established by Co-[name]. Either [name], [name], [name], or [name] all licensed clinical psychologists, will be notified and review the safety plan. In all cases, if families are in treatment at the CSC, or a mental health clinic, a mutually agreeable plan will be derived with the CSC clinical team. In the event of an acute crisis, patient will be transferred to the Rhode Island Hospital (RIH) psychiatric Emergency Department, where all the PI and Co-Investigators [name] and [name] have staff appointments and clinical privileges (See **Human Subjects**).

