**Psychotic symptoms.** The *Structured Interview for Psychosis-risk Syndromes* (SIPS) is a semi-structured interview targeting interviewees' experiences of attenuated symptoms and other indicators of psychosis risk. The SIPS takes approximately 45-90 minutes to complete and assesses the presence of positive, negative, disorganized, and general symptoms. Respondents are determined to meet criteria for psychosis-spectrum disorders/syndromes based on their endorsement and description of five positive symptoms including odd or delusional thoughts, paranoia/suspiciousness, grandiosity, perceptual abnormalities, and disorganized communication. Factors such as the frequency and intensity of positive symptoms, along with the level of conviction (belief that the experience is real) and interference (i.e. associated distress or impairment), are used to determine whether individuals meet criteria for full-threshold psychosis or any of three risk syndromes. The SIPS is the most widely-used psychosis-risk assessment in North America; it has been used to identify individuals with significantly elevated risk for psychosis. Additionally, the SIPS is designed to consider comorbid disorders that may better account for symptoms that could, in isolation, be conceptualized as psychosis-spectrum. The MINI will be completed prior to the SIPS so that comorbid diagnoses will be available. Elevations on the symptom scales of the BPM will also be available and will inform specific SIPS prompts to help with differential diagnosis considerations. In addition, in order to ensure collection of reliable and valid data from the SIPS, Co-I [name] will audiotape interviews, with participant permission, and she will present the case to two of the Investigators on the study. Differential diagnoses will be discussed as well as whether symptoms might be better explained by other disorders.

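### At follow-up the assessors are masked to care received but not to study phase, so rater expectation (and drift, unless baseline SIPS is adjusted for) is aliased with the Aim 3B phase coefficient

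*Combined protocol and SAP*

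**What the plan says.** All references are to the combined protocol and SAP.

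- **Claim of rigor (Significance).** The list of safeguards includes "study retention procedures, blinding of research assessors, data analytic strategies including missing data procedures" and points to the Approach section for detail.
- **Scope of the blind (Baseline and follow-up assessment).** The RA and a co-investigator, whom the next paragraphs show to be the SIPS rater, "will be blind as to whether the families were seen for follow-up CSC or mental health care until after the interviews are completed". To maintain this, they "will instruct families not to disclose whether they followed through with the referral to the CSC" or received other care until the assessment is over. At baseline the rater is masked "to whether youth have screened positive or negative". Neither statement mentions phase or condition.
- **One rater (same section).** "She will administer all the SIPS interviews in order to maintain consistency across the two phases of the study as well as across participants". On reliability, "she was trained to research quality reliability (ICC>.8) within her prior research team". No recheck of agreement within this study is described.
- **Case review (Psychotic symptoms).** The rater "will audiotape interviews, with participant permission, and she will present the case to two of the Investigators on the study", to discuss differential diagnosis. Separately, the section on duration of untreated illness has a consensus meeting that combines SIPS onset with treatment dates to set DUI and DUP.
- **Design (Intervention condition overview; Timeline).** "the two conditions will be compared using a non-randomized open trial design". Follow-up is in months 6-17 for standard care and months 23-34 for enhanced referral.
- **Analysis (Aim 3B).** The main outcomes are SIPS symptom scores, diagnosis and trajectory, all set by the rater. Symptoms are regressed on condition, adjusting for sex, gender, race, ethnicity, age, past history of psychosis-spectrum symptoms and ongoing treatment. The coefficient is to be read as the size and significance of the effect of treatment. The same section says that estimating an effect size is not the pilot's goal.

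**The concern.** The Aim 3B comparison rests on a semi-structured, clinician-rated score. The rater is a study co-investigator who knows, from the calendar alone, which condition each youth was in. If she expects the enhanced phase to do better, or if her scoring changes over time, the shift enters the phase coefficient. Using one rater removes differences between raters, but it can neither reveal nor correct change within that rater. The plan's caveat about secular trends covers which youth are referred and how they answer. It does not cover the rater.

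There is a second route. Care received is withheld until the interview or assessment is completed, but no step fixes the SIPS scores, diagnosis and trajectory at that moment. Treatment information then becomes available and cases are discussed.

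What is at stake is the interpretation of one coefficient, and with it any statement from this pilot that enhanced referral reduced symptoms.

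**Working it through.** **1. Can the rater infer the phase?** The follow-up windows are months 6-17 and 23-34. They share no month. The gap is months 18-22, five months. The midpoints are (6+17)/2 = 11.5 and (23+34)/2 = 28.5, so 17 months apart. Date determines condition without error.

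**2. Is the rater effect separable?** Take a model with an intercept, phase, and a rater shift that differs by phase. The last two columns are identical, so the design matrix has rank 2 of 3. Next add baseline SIPS as a repeated measure: intercept, visit, phase, phase × visit, and an expectation effect acting at follow-up in Phase II. The last two columns coincide, giving rank 4 of 5. Expectation at follow-up stays aliased whatever is adjusted for. Drift that is constant within a phase also affects that phase's baseline ratings, so baseline adjustment can absorb part of it.

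**3. The plan's sample size.** 900 × 0.11 = 99 positive screens a year; 99 × 0.70 = 69.3 (stated 70); 70 × 0.80 = 56 per phase (stated about 55); 140 × 0.80 = 112 (stated 110). These reproduce. I use 55 per phase.

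**4. Illustration of size.** The documents give no alpha, sidedness, shift or correlation for this comparison. I assume a two-sided 5% normal test, no true effect, and a between-phase shift d in SD units.

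Unadjusted: SE = √(2/55) = 0.191. The rejection probability is 1 − Φ(1.96 − d/SE) + Φ(−1.96 − d/SE).

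| d | rejection |
|---|---|
| 0.1 | 8% |
| 0.2 | 18% |
| 0.3 | 35% |

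Adjusted for baseline SIPS with pre-post correlation r, SE = 0.191 × √(1 − r²):

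| d = 0.3 | r = 0.5 | r = 0.7 |
|---|---|---|
| Drift constant within phase: remaining bias d(1 − r) | 0.15 SD | 0.09 SD |
| Rejection | 15% | 10% |
| Expectation at follow-up only: remaining bias | 0.30 SD | 0.30 SD |
| Rejection | 44% | 60% |

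Baseline adjustment helps with drift. It does not reduce follow-up expectation, and because the SE shrinks, the false-positive rate rises.

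**5. What is little affected.** A 0.3 SD shift between equal phases inflates the pooled SD by √(1 + 0.3²/4) = 1.011, about 1%. A true pre-post correlation of 0.5 becomes (0.5 + 0.0225)/1.0225 = 0.511 if the shift is at both visits, or 0.5/√1.0225 = 0.494 if at follow-up only. Aim 2A linkage is not rated on the SIPS.

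**6. Would masked re-scoring of tapes settle it?** Assume an ICC of 0.8. The difference between two ratings then has SD √(2 × 0.2) = 0.63. With 15 or 20 tapes per phase, the SE of the phase contrast is 0.63 × √(2/15) = 0.23 or 0.63 × √(2/20) = 0.20, so the 95% half-width is about 0.45 or 0.39 SD. Power to detect a 0.2-0.3 SD shift is 14-32%.

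**The case against.** The strongest reply is that this is a planning pilot. Aim 3B says that effect size is not its goal and names the SIPS SD, the pre-post correlation and R² as the key parameters. The sequential design is openly justified. This stands, and it limits the point to the phase coefficient. It does not remove the point, because the same section plans an analysis consistent with testing for fewer symptoms in the enhanced phase and reads the coefficient as a treatment effect.

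Three stronger readings are tempting, and the documents do not support them.

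- A reader might infer that the Significance section misstates the blinding. It refers forward to the Approach section, which says exactly what is masked. The summary is incomplete rather than false.
- A reader might infer that drift is beyond any analysis. The same rater scores baseline SIPS in both phases, so baseline adjustment can remove part of a drift that is constant within a phase. The listed covariate for past history may or may not be that score. A baseline difference between phases could also reflect case mix, so the separation is partial.
- A reader might infer that SIPS scores are revised in the light of treatment information. The case presentation concerns differential diagnosis and does not mention treatment. The consensus meeting sets DUI and DUP, which need treatment dates by definition. Neither is said to re-score symptoms. What can be said is that no step prevents it.

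Taping and case review are real safeguards of rating quality. However, the rater herself presents the cases, and no phase-masked re-rating is specified.

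**Conclusion.** The concern holds for the Aim 3B phase coefficient. Assessors are masked to care received and not to phase. Expectation at follow-up is fully aliased with that coefficient. Drift is aliased with it in the model as written unless baseline SIPS is included, and is then only partly removed. SIPS ratings are also not fixed before treatment information and case discussion become available.

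The size is unknown. The 18% and 35% figures depend on an assumed shift of 0.2 or 0.3 SD, 55 per phase and an unadjusted two-sided 5% test, whereas the plan specifies covariate-adjusted regression. They show how sensitive the comparison would be and should not be read as this trial's expected error rate.

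Aim 2A is unaffected, the SIPS SD and pre-post correlation are little affected, and no sample size changes.

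**What to change.** 1. **Lock the ratings.** In the Baseline and follow-up assessment section, require that the rater's follow-up SIPS symptom scores, diagnosis and trajectory are locked in REDCap before the CASA or other treatment items are opened and before any case presentation or consensus meeting. Log any later change separately, so that the locked rating remains available for analysis.
2. **State the limit of the blind and adjust the reporting.** In Significance and Aim 3B, say that assessors are masked to care received but not to phase. Name baseline SIPS score as a covariate. Report the Aim 3B coefficient as a between-phase difference that may include rater expectation or drift, and drop its reading as the size and significance of a treatment effect.

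Both are changes of wording and form order in a system already in use. They need no new visit, rater or participant.

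Masked re-scoring of existing tapes is optional. At 15-20 per phase it is too imprecise to rule out a 0.2-0.3 SD shift. The investigators have already heard the cases, SIPS certification is documented for one person only, and re-scoring cannot undo expectation in how questions were probed. The youth and caregiver BPM is a useful supporting outcome that does not depend on the SIPS rater, but it covers internalizing, attention and externalizing problems and cannot verify a SIPS difference.

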### **1. Background variables (obtained at baseline only).**

Standard demographic variables including age, sex, race, ethnicity, and education will be assessed, including gender identity. Gender identity will be assessed using items listed in “Current Measures of Sexual Orientation and Gender Identity in Federal Surveys, August 2016”. Specifically, we will ask “Do you currently describe yourself as male, female, or transgender?” If transgender, we will ask “Just to confirm, you were assigned [M or F] at birth and now describe yourself as [M or F], is that correct?” Legal history, as well item-level responses on the MAYSI-2 and PQ-B, will be obtained from JID records as part of the consent process. The collection of much of the data from legal records and existing JJ system procedures is an additional strength of this service-based application as it improves feasibility and the potential for scalability in the future.

### **2. CMIR implementation level measures**

These data will be collected and measures will be administered to JID staff and administrators at the conclusion of Phase II of the project.

**Feasibility** will be defined as the percent of youth who screen positive on the MAYSI-2 Thought Disturbance subscale and/or PQ-B who receive the Enhanced Referral/Linkage to Care protocol in Phase II of the project. Follow-up rates of texting/phone calls will also be examined separately with respect to its feasibility.

**Penetration** will be measured by the percent of *personnel* who are trained to deliver the Enhanced Referral/Linkage to Care condition brief intervention.

**Acceptability** will be assessed using qualitative interviews with JJ staff related to their perceived roles in screening and using the Enhanced Referral/Linkage to Care protocol. In addition, the *Attitudes Toward Mental Health Screening*, a 15-item scale that assesses clinician’s attitudes towards and self-efficacy in relation to screening and intervention, will be administered at baseline and follow-up. The measure has 4 subscales: positive attitudes, level of confidence, perceived barriers, and role congruence towards mental health screening. Staff rate each item on a five-point scale from “not at all” to “a very great extent”.

### **3. CMIR service-level measures**

**Fidelity** will be assessed using the rating procedure described above. Fidelity will also be considered a marker of the quality of treatment linkage in conjunction with the percent of referrals completed to the CSC.

**Efficiency** will be rated by the number of text message and phone contacts necessary to complete the referral to the CSC.

**Equity** will be measured by examining differences by sex/gender and racial/ethnic subgroups in the numbers of at-risk youth who receive the Enhanced Referral/Linkage to Care condition, fidelity/quality of the Enhanced Referral/Linkage to Care protocol, and actual completion of the referral to the CSC.

